4.2.5. Severity

- (1) Mild: Awareness of signs or symptom, but easily tolerated.
- (2) Moderate: Discomfort, enough to cause interference with usual activity.
- (3) Severe: Incapacitating with inability to work or perform usual activity.

4.3. Demographics and Disease Characters

4.3.1. Demographics

The demographics including age, sex, and nation will be recorded in CRF.

4.3.2. Medical History

The information of medical history including disease name, start date, end date and ongoing will be recorded in CRF.

4.3.3. Surgery History

The name and date of surgery prior to screening will be recorded in CRF.

4.3.4. Allergy History

The information of allergy history will be recorded in CRF.

4.4. Prior/Concomitant Medication

The information of prior/concomitant medication including drug name, dose, unit, frequency, route of administration, start date, end date, ongoing, and reason for usage will be recorded in CRF.

4.5.Prior/Concomitant Treatment

The information of prior/concomitant treatment including name of treatment, start date, end date, ongoing, and treatment reason will be recorded in CRF during the study.

4.6.Protocol Deviation

Clinical operation team shall record the cause, date and severity of all protocol deviations in the file Protocol Deviation Tracking Log.

5. STATISTICAL HYPOTHESIS

Not applicable. This is a non-interventional study.

6. ANALYSIS SETS

6.1.Full Analysis Set (FAS)

All subjects screened, enrolled in the study treated at least once with Dysport.

6.2.Per Protocol Set (PPS)

A subset of FAS that include subjects who have evaluable primary efficacy endpoints, have overall good compliance, and have no major protocol deviations during the study. Subjects excluded from PPS will be determined in Data Review Meeting before Data Base Lock.

6.3.Safety Set (SS)

The set of subjects who have received at least one dose of study treatment and for whom actual data on safety endpoints are available.

7. STATISTICAL METHODS

7.1.General Statistical Consideration

Demographics and disease characteristics data, efficacy data, and safety data will be analyzed. The annotated or explanatory transcript will only be listed. The following rules apply to general situations unless otherwise stated.

7.1.1. Application of Analysis Sets

Baseline analyses will be based on FAS and PPS; efficacy analyses will be primarily based on PPS, and on FAS as reference; safety analyses will be based on SS.

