10.1.2 Populations Analyzed and Evaluability

The primary analysis will be performed on the enrolled population. Analysis on the per-protocol (PP) population maybe performed, if needed.

The rules for the allocation of subjects to each of the analysis populations will be defined and documented during a data review meeting held prior to database lock.

During the data review meeting, based on minor or major protocol deviations recorded, subjects may be excluded from the PP population.

Subjects may be excluded from the analyses if one or more of the following deviations occur.

- Subject did not complete the study
- Violation of inclusion/exclusion criteria

10.1.2.1 *Enrolled Population*

The enrolled population includes all subjects who are enrolled in the study treated at least once with *Dysport*.

10.1.2.2 *Per-protocol (PP) Population*

The Per Protocol (PP) population is a subset of the enrolled subjects who have no major protocol deviations, as outlined above.

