Appendix 1 Subject Satisfaction Questionnaire

Subject #:

Visit #:

Date of questionnaire completion (DD/MM/YYYY):

Please tick the box corresponding to your preferred answer (only one box should be ticked by question unless otherwise specified).

Complete at Visit 1 ONLY

CCI

4. How satisfied have you been with the aesthetic outcome in the injected area after treatment?

[figure not shown]
- Very satisfied
- Satisfied
- Dissatisfied
- Very dissatisfied

5. How satisfied were you with the comfort of the injection?

- Very satisfied
- Satisfied
- Dissatisfied
- Very dissatisfied

Effective

Effective date: 2021-06-28 08:30

Effective date: 2021-06-28 08:30

CCI

Effective**Complete at Visit 6 ONLY****17. What is your overall satisfaction after three treatment cycles with *Dysport*?**

- Very satisfied
- Satisfied
- Dissatisfied
- Very dissatisfied

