7.4. Efficacy Analysis

7.4.1. Analysis on Primary Efficacy Endpoints

Analysis on primary efficacy endpoints will be performed on PPS and FAS.

[figure not shown]
At Visit 6 proportion of subjects in each response category from subject satisfaction will be evaluated and its exact 95% CI will be calculated.

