7.4.2. Analysis on Secondary Efficacy Endpoints

Analysis on secondary efficacy endpoints will be performed on PPS and FAS.

- ① At Visit 6 proportion of subjects in each response category from physician overall satisfaction will be evaluated and its exact 95% CI will be calculated.
- ② a. At all visits proportion of subjects in each response category per question from subject satisfaction will be evaluated and its exact 95% CI will be calculated.

CCI

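### The SAP makes the per-protocol set lead the efficacy results, an undeclared reversal of the protocol that drops early-visit answers from subjects who later left

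*SAP*

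**What the plan says.** Protocol 10.1.2: "The primary analysis will be performed on the enrolled population. Analysis on the per-protocol (PP) population maybe performed, if needed". The enrolled population is defined there as enrolled subjects treated at least once. The SAP's FAS (section 6.1) has the same content.

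SAP 7.1.1 sets the opposite order: "efficacy analyses will be primarily based on PPS, and on FAS as reference". SAP 7.4.1 says "Analysis on primary efficacy endpoints will be performed on PPS and FAS", and 7.4.2 uses the same pair for the secondary endpoints. Neither section says which set leads, so 7.1.1 governs.

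SAP 6.2 defines PPS as "A subset of FAS that include subjects who have evaluable primary efficacy endpoints, have overall good compliance, and have no major protocol deviations". The primary endpoint is Question 17 of the Subject Satisfaction Questionnaire, marked in Protocol Appendix 1 as "Complete at Visit 6 ONLY". SAP 7.4.2 also plans tables for the whole questionnaire: "At all visits proportion of subjects in each response category per question from subject satisfaction will be evaluated".

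Under SAP 7.1.2 and 7.2, percentages use non-missing data and nothing is imputed. SAP 7.6 adds interim analyses after Visit 2 and after Visit 4. SAP 7.7 lists three changes from the protocol: the interim analyses, the removal of the adverse drug reaction definition, and the rewording of unexpected reactions as unexpected events. The change of leading population is not among them.

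**The concern.** The two governing documents name different leading populations, and the report cannot lead with both. A reader who trusts SAP 7.7 would not know that anything had changed.

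The consequence differs by result.

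- **Earlier-visit questionnaire tables.** Membership of the leading set depends on something that happens later, a Visit 6 answer. Someone who answered at Visit 2 and then stopped treatment is removed from the leading Visit 2 table although the answer exists. In a study meant to describe satisfaction in real practice, people who stop are part of what is being described. If they were less satisfied, early satisfaction is overstated.
- **Interim analyses.** PPS needs a Visit 6 answer and is settled at a data review meeting before database lock, so it cannot be formed after Visit 2 or Visit 4. SAP 7.6 names no other set. Early results would presumably appear first on FAS and later be led by a different set.
- **Primary endpoint.** Here the switch matters little, because FAS percentages are also limited to subjects who answered at Visit 6. Neither set, as planned, shows the response categories as a share of everyone treated.

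**Working it through.** The documents contain no figure to reproduce. The sample size of about 250 is stated not to rest on a calculation, there is no hypothesis, and no dropout or satisfaction rate is given. The check is therefore first textual, then illustrative.

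**Text, side by side**

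| Item | Protocol | SAP |
|---|---|---|
| Leading set | Enrolled population (10.1.2) | PPS (7.1.1) |
| Other set | PP, optional (10.1.2) | FAS, as reference (7.1.1) |
| Switch declared? | – | Not in 7.7 |
| PPS needs a Visit 6 answer? | Not stated for PP | Yes (6.2, with Question 17 asked at Visit 6 only) |

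**Earlier-visit item, illustration**

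Assumptions: 250 treated, all answer at Visit 2, a share L leaves before Visit 6, PPS loses only those leavers, 95% of stayers are satisfied, and a proportion s of leavers is satisfied.

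- FAS proportion = (1 − L) × 0.95 + L × s
- PPS proportion = 0.95
- Overstatement = L × (0.95 − s)

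With L = 0.20 and s = 0.60:

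- 50 leavers, of whom 30 are satisfied; 200 stayers, of whom 190 are satisfied.
- FAS: 220/250 = 88.0% (exact 95% CI 83.3 to 91.8).
- PPS: 190/200 = 95.0% (91.0 to 97.6).
- Gap: 0.20 × (0.95 − 0.60) = 7.0 percentage points.

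Overstatement in points over a range of assumptions:

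| L | s = 0.95 | s = 0.70 | s = 0.60 | s = 0.30 |
|---|---|---|---|---|
| 0.10 | 0 | 2.5 | 3.5 | 6.5 |
| 0.20 | 0 | 5.0 | 7.0 | 13.0 |
| 0.30 | 0 | 7.5 | 10.5 | 19.5 |
| 0.40 | 0 | 10.0 | 14.0 | 26.0 |

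**Question 17**

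With 50 of 250 giving no Visit 6 answer and 190 of the 200 responders satisfied, the non-missing percentage is 190/200 = 95.0% on both sets. They can differ only if some Visit 6 responders are excluded for compliance or major deviations, or for non-completion if the protocol's ground is applied. If a share e of responders is excluded, s of them are satisfied and 95% of those kept are satisfied, PPS exceeds FAS by e × (0.95 − s). For e from 0.05 to 0.20 and s from 0.75 to 0.95, this is 0 to 0.20 × 0.20 = 4.0 points.

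As a share of all treated, 190/250 = 76.0% (70.2 to 81.2). With responders still about 95% satisfied (counts rounded):

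| No Visit 6 answer | Satisfied, of all 250 treated |
|---|---|
| 25 | 214/250 = 85.6% |
| 50 | 190/250 = 76.0% |
| 75 | 166/250 = 66.4% |
| 100 | 142/250 = 56.8% |

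This share counts every non-responder as not satisfied. It is a floor, not an estimate of satisfaction.

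**The case against.** The strongest case on the other side has four parts.

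**Nothing is lost.** The study is descriptive, both sets are analysed for the primary and secondary endpoints, and SAP 7.3.1 and 7.3.3 tabulate discontinuations and set exclusions with reasons. This is correct and limits the point to which result leads and whether the change is declared. It does not make the two documents agree.

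**The protocol is not entirely clean.** It also says "Subjects may be excluded from the analyses if one or more of the following deviations occur", and one listed ground is "Subject did not complete the study". It leaves allocation rules to the data review meeting, and it does not expressly assign a population to the secondary tables. So some removal of non-completers was foreseen, and the reversal is plainest for Question 17, where it matters least. But this text governs who belongs to a set, not which set leads, and nothing in the protocol gives the per-protocol population a leading role for any endpoint.

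**The interim point may be harmless.** SAP 7.6 limits the interims to applicable output, so a PPS table that cannot be formed can be read as not applicable. That softens the point, but the SAP still names no usable set.

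**The size is hypothetical.** This stands. The upper end of 26 points needs 40% leaving and only 30% of leavers satisfied; zero is possible. Most of the questionnaire is redacted and the table shells are not available, so the wording of Visit 2 items cannot be checked and a missing-answer row may already exist in the shells.

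**Conclusion.** The concern holds. SAP 7.1.1 reverses the protocol's leading population, SAP 7.7 does not declare it, and PPS membership depends on a Visit 6 answer. These three facts rest on the text alone. The resulting selection affects the leading earlier-visit tables. Its size depends wholly on assumed rates: 7 points in the worked case, 2.5 to 26 points with 10–40% leaving and 30–70% of leavers satisfied against 95% of stayers, and zero if leaving is unrelated to satisfaction. For Question 17 the effect of the switch is 0 to 4 points under the stated exclusion assumptions. The Visit 6 condition itself contributes nothing there. This needs correcting before the analysis, because the leading result is otherwise undetermined between the two documents.

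**What to change.** **Essential:** in SAP 7.1.1, 7.4.1 and 7.4.2, make FAS (the protocol's enrolled population) primary and PPS supportive. If the sponsor prefers PPS to lead, declare and justify it in SAP 7.7.

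**Accompanying changes:**

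- SAP 7.6: name FAS as the set for both interim analyses.
- SAP 7.4.1: for Question 17, report the number of treated subjects with no Visit 6 answer, with reasons, and give each category as a percentage of all treated subjects beside the non-missing percentage.
- SAP 6.2: limit the Visit 6 answer condition to the Visit 6 overall-satisfaction tables.
- SAP 6.1: state that non-completion does not remove a treated subject from FAS. The protocol's ground is permissive, so the SAP may say this.

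The last two are largely redundant once FAS leads, but the 6.2 change becomes important if PPS is kept as primary.

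The cost is SAP wording, one extra denominator and one missing-answer row. No new data are needed. Leading early-visit figures may be less favourable; the non-missing Question 17 figure should change little.

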7.1.2. Descriptive Statistics

For continuous data, descriptive statistics include number of non-missing patients, number of missing patients (nmiss), mean, standard deviation (SD), median, Q1, Q3, minimum, and maximum.

For categorical data, the frequency and percentage of patients in each category will be presented. Counts that are zero will be displayed as “0”. Percentages will be based on non-missing data unless otherwise specified. Two-sided 95% confidence interval will be calculated for the estimated incidence wherever appropriate.

7.1.3. Decimals

The minimum and maximum will keep the same decimal place with the raw data, while mean, median, Q1 and Q3 will keep 1 more decimal place, and SD will keep 2 more decimal places. The decimal place of above statistics will not exceed 4 regardless of the decimal place of raw data.

Percentages and 95% confidence interval (CI) will keep 1 decimal place.

P value will be rounded to 4 decimal places. ‘<.0001’ will be displayed when the P value is lesser than 0.0001 and ‘>.9999’ will be displayed when the P value is greater than 0.9999.

7.1.4. General Statistical Test Methods

For continuous data, parametric or non-parametric method will be used according to the result of Shapiro-Wilk test with 5% significance level.

For within-group comparison, paired t-test will be performed if the assumption of normality is satisfied, otherwise Wilcoxon signed rank test will be performed.

For between-group comparison, two sample t-test will be performed if the assumption of normality is satisfied, otherwise Wilcoxon rank sum test will be performed.

For between-group comparison of categorical data, chi-square test will be basically performed and the Wald asymptotic 95% confidence interval will be calculated.

But in case of more than 20% of the number of cells with an expected frequency of less than 5, Fisher’s exact test will be performed and the exact 95% confidence intervals will be calculated.

7.1.5. Significance Level

Statistical analysis will be performed with a two-sided test at a significance level of 5% whenever required.

7.1.6. Software for Statistical Analysis

Statistical programming will use SAS® 9.4 or higher version.

7.1.7. Definition of Baseline

The baseline values for all variables (if applicable) are defined as the latest measurement or examine result before injection.

7.1.8. Scheduled and Unscheduled Visit

Generally, statistical description by visits will be performed on the scheduled visits unless it is specified otherwise. For shift table of clinical evaluation of safety data, the data on scheduled and unscheduled visits will be all included in the analyses.

7.1.9. Subject Identifier

For the data listing, screening number (USUBJID) will be used as a unique identifier.

7.2. Data Handling

Data will be analyzed as observed without imputation for missing values.

7.3. Subjects in Study

7.3.1. Subjects Disposition

The following summaries will be tabulated:

- No. and percentage of subjects screened and reasons for screening failure
- No. and percentage of subjects who are treated and not treated.
- No. and percentage of subjects who completed the study.
- No. and percentage of subjects who prematurely discontinued study and reasons of early termination

The above analysis will be summarized for each site.

Detailed information regarding disposition of each subject will be listed.

7.3.2. Protocol Deviation

For all enrolled subjects, all major protocol deviations recorded by clinical operation team will be summarized according to predefined categories. All the protocol deviations will be recorded in the file Protocol Deviation Tracking Log.

Major protocol deviations will be summarized for each site.

All protocol deviations recorded by clinical operation team of each subject will be listed.

7.3.3. Analysis Sets

For all enrolled subjects, the number of subjects in each analysis set will be summarized together with the number of subjects excluded from each analysis set and the corresponding reasons.

The above analysis will be summarized for each site.

Detailed information of analysis sets will be listed.

7.3.4. Demographics and Baseline Characters

- **Demographics**

The demographics including age, sex, and nation will be summarized using descriptive statistics.

Detailed information of demographics will be listed by subject.

- **Medical/ Surgery History**

Number of events, number and percentage of subjects who had at least one medical history will be summarized using descriptive statistics. All medical history will also be summarized by System Organ Class (SOC) and preferred term (PT) that will be coded using the MedDRA version 25.1.

Detailed information of medical/surgery history will be listed by subject.

7.3.5. Allergy History

Number of events, number and percentage of subjects who had at least one allergy history will be summarized using descriptive statistics. The number of events will also be presented.

Detailed information of allergy history will be listed by subject.

7.3.6. Prior/Concomitant Medication

Prior medication and concomitant medication analyses will be based on FAS and PPS.

Prior medication and concomitant medications will be coded by the World Health Organization Drug Dictionary (WHO DD) Global (B3) E [V2022SEP]. Prior and concomitant medications will be summarized by Anatomical Therapeutic Chemical (ATC) classification (including Anatomy group, Therapeutic group and Chemical group) and WHO preferred drug name, respectively. The summary will be sorted in decreasing order of percentage of ATC class firstly and then sorted in decreasing order of percentage of preferred drug term within the ATC class.

Prior medications: if the end date of the medication is before the date of injection in this study.
Concomitant medications: if the end date of the medication is on or after the date of injection in this study or still ongoing.

Detailed information of prior and concomitant medications will be listed by subject.

7.3.7. Prior/Concomitant Treatment

Prior and concomitant treatment analyses will be based on FAS and PPS.

Number of events, number and percentage of subjects who had at least one treatment will be summarized using descriptive statistics.

All prior/concomitant treatment will be coded by MedDRA version 25.1 and summarized by SOC and PT.

Detailed information of prior/concomitant treatment will be listed by subject.

7.4. Efficacy Analysis

7.4.1. Analysis on Primary Efficacy Endpoints

Analysis on primary efficacy endpoints will be performed on PPS and FAS.

[figure not shown]
At Visit 6 proportion of subjects in each response category from subject satisfaction will be evaluated and its exact 95% CI will be calculated.

7.4.2. Analysis on Secondary Efficacy Endpoints

Analysis on secondary efficacy endpoints will be performed on PPS and FAS.

- ① At Visit 6 proportion of subjects in each response category from physician overall satisfaction will be evaluated and its exact 95% CI will be calculated.
- ② a. At all visits proportion of subjects in each response category per question from subject satisfaction will be evaluated and its exact 95% CI will be calculated.

CCI

7.5. Safety Analysis

AEs will be coded by MedDRA version 25.1. SOC and PT will be presented in summary tables of AE. All summary table will be based on Treatment Emergent AE (TEAE).

TEAE defines as all AEs that occur after the first treatment.

Overall TEAEs, UAEs, SAEs, SS Events, AEs leading to discontinuation from study, AEs leading to death and whether these AEs are possibly caused by the product and/or injection procedure, will be summarized by number of events, number of subjects, percentage and 95% CI.

The number of events, number of subjects and percentage with AEs and product and/or injection procedure related AEs will be summarized for each category by SOC, PT and severity. If multiple

AEs in the same SOC (PT) have occurred in the same subject when summarizing the number of subjects, the subject will be counted only once for this SOC (PT). When summarizing the number of subjects by severity, if multiple AEs in the same SOC (PT) have occurred in the same subject, the event with the highest severity of this SOC (PT) will be used for analysis. When summarizing the number of events, all the AEs will be accounted.

Detailed information of AEs, UAEs, SAEs, SS Events, AEs possibly caused by the product and/or injection procedure, AEs leading to discontinuation, and AEs leading to death will be listed by subject.

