8 SAFETY ASSESSMENTS

AEs will be recorded in the eCRF for inclusion in the clinical database.

In addition, physicians will report all AEs non-serious, serious, and/or unexpected ADRs, and SS events to **CC1** in accordance with regulatory reporting requirements and timelines. The data will be included in the global drug safety database.

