8.1.5 Special Situation (SS) Events

A Special Situation (SS) event is an incidence of overdose, off-label use, medication error, occupational exposure, abuse, misuse or lack of therapeutic efficacy while using the medicinal product, or any instance of drug exposure during pregnancy or breast-feeding. A SS should be reported even if it is not associated with an adverse event.

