8.4 Reporting Procedures

AE data will be recorded in the eCRF for inclusion in the clinical database and will be reported to CCI [REDACTED].

In addition, any ADR/UADR/SAE/SS and pregnancy must be reported immediately (within 24 hours of the physician's knowledge of the event) to the following:

CCI [REDACTED]

See [Investigator and Administrative Structure](#) for additional contact information.

In order to facilitate this reporting, the physicians will be provided with Adverse Event and Special Situation Reporting Form. If the immediate report is submitted by telephone, this must be followed by detailed written reports using the Adverse Event and Special Situation Reporting Form.

 GALDERMA		
---	--	--

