4.2.4. Special Situation (SS) Events

SS Event is an incidence of overdose, off-label use, medication error, occupational exposure, abuse, misuse, or lack of therapeutic efficacy while using the medicinal product, or any instance of drug exposure during pregnancy or breast-feeding.

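### SAP 7.5 is inconsistent on Special Situation events: it summarises them, yet bases all summary tables on treatment-emergent AEs, which read literally leaves out those without an AE

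*SAP*

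**What the plan says.** SAP 7.5 sets one basis for safety tables: "All summary table will be based on Treatment Emergent AE (TEAE". It then defines the term: "TEAE defines as all AEs that occur after the first treatment". The next paragraph gives the contents of the overall summary: "Overall TEAEs, UAEs, SAEs, SS Events, AEs leading to discontinuation from study, AEs leading to death and whether these AEs are possibly caused". Each item is to have a number of events, a number of subjects, a percentage and a 95% CI. The section closes with by-subject listings: "Detailed information of AEs, UAEs, SAEs, SS Events, AEs possibly caused by the product and/or injection procedure". No treatment-emergent limit is stated for the listings.

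SAP 4.2.4, under the safety endpoints, gives the definition: "SS Event is an incidence of overdose, off-label use, medication error, occupational exposure, abuse, misuse, or lack of therapeutic efficacy". It also covers drug exposure during pregnancy or breast-feeding. Protocol 8.1.5 has the same definition and adds: "A SS should be reported even if it is not associated with an adverse event". SAP 4.2.4 does not carry that sentence over.

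On data flow, protocol 8.4 says "AE data will be recorded in the eCRF for inclusion in the clinical database". For reports made to pharmacovigilance, which include Special Situation events, protocol section 8 says "The data will be included in the global drug safety database".

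**The concern.** A Special Situation event is a wider concept than an AE: a dosing error in a subject who stays well qualifies as the former and not the latter. A table restricted to TEAEs cannot hold such an event. SAP 7.5 therefore promises a statistic for a stated safety endpoint under a counting rule that does not fit the endpoint's definition.

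Two programmers could follow the same plan and produce different Special Situation rows. The literal route can only give the lower figure. This is a study of real-practice use that records dose, volume, muscles and injection points at every injection visit, so a row near zero beside records showing departures would be awkward to explain.

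**Working it through.** The documents give no Special Situation count or rate, so there is no plan figure to reproduce. The check is mainly textual, followed by an illustration on assumed counts.

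**Step 1. The two readings of SAP 7.5.**

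- *Literal reading.* The rule covers all summary tables and makes no exception for Special Situation events. The overall-summary sentence, after naming them, refers back to everything listed as AEs. On this reading an event without an AE adds 0 to the row.
- *Separate-item reading.* Special Situation events stand beside TEAEs in that list, not under them, and SAP 4.2.4 makes them an endpoint of their own. On this reading the same event adds 1.

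No sentence in the SAP chooses between the two.

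**Step 2. The first injection.** The TEAE definition requires occurrence after the first treatment. A dosing error at Visit 1 occurs during that treatment. If the TEAE definition governs the row, it is unclear whether the error counts, even if an AE follows later.

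**Step 3. Direction.** Understatement = Special Situation events with no AE + any linked to an AE but not counted as after the first treatment. Both terms are zero or positive, so the literal rule never overstates.

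**Step 4. Illustrative size.** Inputs:

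- n = 250, the approximate planned number (protocol 10.2, SAP 3.6), assuming all are treated and in the Safety Set;
- x = number of subjects with a Special Situation event (assumed);
- exact (Clopper-Pearson) interval, also an assumption because SAP 7.5 does not name a method: lower limit = Beta quantile 0.025 with parameters (x, n − x + 1); upper limit = Beta quantile 0.975 with parameters (x + 1, n − x).

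With 10 affected subjects:

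| Affected subjects without an AE | Counted under literal rule | Percentage | 95% CI |
|---|---|---|---|
| none | 10/250 | 4.0% | 1.9 to 7.2 |
| half | 5/250 | 2.0% | 0.7 to 4.6 |
| all | 0/250 | 0.0% | 0 to 1.5 |

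The first row is also the full count under the separate-item reading. In the last row the interval excludes the full-count value of 4.0%.

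For 5 affected subjects the full count is 5/250 = 2.0% (0.7 to 4.6). For 25 it is 25/250 = 10.0% (6.6 to 14.4). In each case the literal count could lie anywhere from 0% up to the full value. The table ignores the Step 2 ambiguity, which could only lower the literal counts further.

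**The case against.** The best defence is context. The TEAE sentence directly follows one about presenting SOC and PT in AE tables, so its natural scope may be those tables. Special Situation events are then named as a separate item, and the SAP 4.2.4 definition contains no AE requirement. This stands to the extent that exclusion is not certain. It does not settle the matter, because the rule is worded to cover all summary tables.

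A reader might infer more than the documents support:

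- *That the protocol requires these events in the summary counts.* It does not. Protocol 8.1.5 sets a reporting duty, which protocol 8.4 makes a 24-hour pharmacovigilance report. No protocol section gives a tabulation rule for Special Situation events.
- *That the SAP narrowed the definition without declaring it in SAP 7.7.* The sentence missing from SAP 4.2.4 is a reporting instruction. Without it the definition still covers events with no AE.
- *That dosing departures would vanish from the report.* Special Situation events and all protocol deviations are to be listed by subject, and injection practice details are collected at Visits 1, 3 and 5. Some secondary endpoints are redacted, so it cannot be said that those details go unanalysed.
- *That the records never reach the analysis data.* AEs also go to pharmacovigilance and are still in the eCRF, so a report to the safety database does not show absence from the clinical database. The eCRF and table shells are not available to check. What can be said is that the SAP text does not name the source.

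The listing is a real mitigation, but it does not correct a reported count, percentage and interval.

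**Conclusion.** The point holds as an internal inconsistency in SAP 7.5. Its literal rule omits Special Situation events that have no AE, and arguably those at the first injection, from the count, percentage and 95% CI of a stated safety endpoint. The effect runs in one direction only.

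The size is unknown. It depends on how many such events occur and what share has no AE, and the documents give neither. If every event comes with an AE after the first treatment, nothing changes. The figures above rest on assumed counts and on 250 treated subjects. The primary endpoint is unaffected. This is a clarification worth making before database lock, not a flaw in the study's main result.

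**What to change.** In SAP 7.5:

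1. Limit the TEAE rule to the AE tables.
2. State that the Special Situation row is based on the Safety Set and counts all such events from the first injection inclusive, whether or not an AE is associated.
3. Reword the overall-summary sentence so that Special Situation events are not referred to as AEs.
4. Name the data source for Special Situation records (eCRF, safety database, or both after reconciliation).
5. Before database lock, check the records for consistency with the injection practice details already collected.

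Carrying the protocol 8.1.5 sentence into SAP 4.2.4 would help the reader but is optional once item 2 is in place.

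The cost is a few lines of SAP text, a little more programming and one consistency check, with no new data collection. The reported Special Situation count may be higher than under the literal rule.
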